12. STATISTICS

12.1. Statistical Analysis Plan (SAP)

The plan for the statistical analysis of the trial are outlined below. There is not a separate SAP document in use for the trial.

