12.2. Description of Statistical Methods

Continuous data will be summarized using descriptive statistics (mean, median, standard deviation, quartiles, minimum and maximum) and categorical data will be summarized using counts and

IRAS ID: 301556

percentages. The proportion of patients undergoing operative compared to non-operative treatment will be reported.

Primary endpoint

The primary endpoint will be reported as the percentage of patients re-admitted with gallstone related problems after operative vs non-operative management during their index admission.

Secondary endpoints

Data will be reported at 30 days, 1 year and 3 years. Patients who have had complications or have died in each group will be reported as a number and percentage. Comparison between groups will be carried out using Chi squared test. Gastrointestinal Quality of Life Index (GIQLI) in each group will be reported as a median and range. Paired T test will be used to compare groups.

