12.3. Sample Size Determination

From previous studies, we estimate an approximate readmission rate of at least 30% in patients who do not have surgery compared to 5% in those who do. We estimate that approximately 10% of patients over 70 will not have surgery therefore the enrolment ratio is likely to be 1:9. Using an alpha of 0.05 and a power of 0.9 the number of patients required would therefore be 260. We would aim to recruit a minimum of 290 patients to account for a maximum of 10% lost to follow up.

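### Section 12.2 plans percentages, a median and range, and p-values, but no between-group difference or confidence interval for any outcome; with as few as 26 non-operative patients a non-significant secondary result may be misread

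*Protocol*

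**What the plan says.** Section 12.1 of the Protocol closes off any later document: "There is not a separate SAP document in use for the trial". Section 12.2 is therefore the analysis plan, and it fixes these formats:

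- **Readmission (primary):** a percentage per group.
- **Deaths and complications:** "Patients who have had complications or have died in each group will be reported as a number and percentage", followed by "Comparison between groups will be carried out using Chi squared test".
- **GIQLI:** "Gastrointestinal Quality of Life Index (GIQLI) in each group will be reported as a median and range", followed by "Paired T test will be used to compare groups".
- **Continuous data in general** (opening sentence of 12.2): "Continuous data will be summarized using descriptive statistics (mean, median, standard deviation, quartiles, minimum and maximum".

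Section 6 words the primary objective and all three secondary objectives as comparisons between operative and non-operative patients. Section 12.3 sizes the study on readmission alone: "we estimate an approximate readmission rate of at least 30% in patients who do not have surgery compared to 5% in those who do", and "the enrolment ratio is likely to be 1:9".

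**The concern.** Each objective asks how far the two groups differ, yet the plan commits to no estimate of that difference and no statement of its precision. The reader gets two group summaries and, for the secondary outcomes, a p-value.

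This matters most where the p-value is least informative. The sample size was chosen for a 25-point difference in readmission. Smaller differences in death, complications or GIQLI can easily be missed when one group is about a tenth of the cohort. Section 2 says the results should help doctors discuss likely outcomes with patients. That needs the size of a difference and the range of values the data allow. A bare non-significant result on mortality may be taken as equal risk.

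The GIQLI sentence has two further faults of its own. The summary named (median) is not the quantity a t test compares (mean). And the spread named (range) tends to grow with group size, so unequal groups show unequal ranges even when their distributions are identical.

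**Working it through.** **Group sizes.** Section 12.3 expects 10% non-operative out of 260 evaluable patients: 0.10 × 260 = 26, leaving 234. The recruitment target agrees: 290 × 0.90 = 261. Section 5 cites up to 30% managed non-operatively, which gives 0.30 × 260 = 78 v 182. Both splits are used below. The 260 is taken as stated. For the allocation described, the usual two-sided pooled formula gives 210 (250 with continuity correction), so 26 v 234 has about 94% power for 30% v 5%. The primary contrast is not what is short of power.

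**Assumptions.** The Protocol gives no rates for death or complications and no GIQLI standard deviation. Illustrative rates are used, with the higher rate in the non-operative group, and GIQLI results are in SD units. Tests are two-sided at 0.05.

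**Power for 20% v 10%.** Power ≈ Φ[(0.10 − 1.96 s0)/s1], where s0 is the pooled and s1 the unpooled standard error.

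| Split | pooled rate | s0 | s1 | approximate power | exact binomial, uncorrected chi-squared |
|---|---|---|---|---|---|
| 26 v 234 | 0.11 | 0.0647 | 0.0809 | Φ(−0.33) = 37% | 36% |
| 78 v 182 | 0.13 | 0.0455 | 0.0505 | Φ(0.21) = 58% | 59% |

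Against 10% in the operative group, 80% power needs about 32% in the other group at 26 v 234, and about 24% at 78 v 182. By the same approximation at 26 v 234, power for a 10-point excess is 52% (15% v 5%), 37% (20% v 10%) and 24% (30% v 20%).

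**What a non-significant p-value can hide: 5/26 v 23/234.**

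- Rates: 5/26 = 0.192 and 23/234 = 0.098; difference 0.094.
- Test: pooled rate 28/260 = 0.108; standard error √[0.108 × 0.892 × (1/26 + 1/234)] = 0.0641; z = 0.094/0.0641 = 1.47; p = 0.14.
- Wilson limits: 0.0851 to 0.3788 and 0.0664 to 0.1432.
- Newcombe lower limit: 0.0940 − √[(0.1923 − 0.0851)² + (0.1432 − 0.0983)²] = −0.022.
- Newcombe upper limit: 0.0940 + √[(0.3788 − 0.1923)² + (0.0983 − 0.0664)²] = +0.283.

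The 95% interval is −2 to +28 points. Even nearly equal rates, 3/26 v 23/234 (p = 0.78), give −7 to +19 points.

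**GIQLI precision.** The standard error of an independent-groups mean difference is SD × √(1/n1 + 1/n2).

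- 26 v 234: 0.207 SD; 95% half-width 1.96 × 0.207 = 0.41 SD.
- 78 v 182: 0.135 SD; half-width 0.27 SD.

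Deaths before the later questionnaires would widen both.

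**Range and group size.** For identical normal distributions, the expected range is ∫[1 − Φ(x)ⁿ − (1 − Φ(x))ⁿ]dx in SD units.

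- 26 v 234: 3.96 and 5.60; ratio 1.41.
- 78 v 182: 4.83 and 5.43; ratio 1.12.

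GIQLI scores need not be normal, so these ratios show the direction and rough size only.

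**The case against.** **The opening sentence of 12.2 already promises mean, SD and quartiles.** This stands in part. Read together, the two sentences do not deprive the reader of a mean or a size-stable measure of spread, and nothing in the plan draws an inference from the range. The GIQLI format is thus a mismatch to be aligned, and it does not invalidate the comparison. Neither sentence supplies a between-group estimate.

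**Intervals can be derived from the published counts.** True for the percentages, so no information is lost there. The plan still does not commit to reporting the interval or to interpreting results from it.

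**The figure of 26 is one scenario.** Correct, and sections 12.2 and 12.4 also differ on whether surgery after the index admission counts as operative, which could change the split. The second scenario is milder, but power of 59% remains poor.

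**The misreading is only inferred.** A reader might conclude that the plan will present a null result as equivalence. No sentence says so; the format permits that misreading and does not prescribe it. Nor does the argument extend to the primary endpoint as designed: 30% v 5% is well powered, and there the gap is only the missing estimate and interval.

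**An interval is not the whole uncertainty.** This stands. Section 2 says that patients not offered surgery are usually elderly, frail or otherwise unwell. An unadjusted interval leaves that confounding untouched.

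**Conclusion.** The point holds as a reporting defect that should be corrected before analysis. Section 12.2 plans no between-group difference or confidence interval for any outcome, and section 12.1 rules out a separate plan that would supply one. The GIQLI sentence also needs aligning with the opening sentence of 12.2 and with a comparison of means.

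For an assumed doubling from 10% to 20%, the secondary comparisons have roughly 36% to 59% power across the Protocol's own 10% to 30% non-operative share. At the lower share, a p-value of 0.14 can sit beside an interval reaching +28 points. These sizes rest on 260 evaluable patients and on assumed event rates. The absence of estimates and intervals does not depend on them.

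The use of a paired test on two separate groups is a different matter. Replacing it would leave this point unchanged.

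**What to change.** In section 12.2:

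1. For readmission, complications and death at 30 days, 1 year and 3 years, report the number and percentage per group and the risk difference with a 95% score (Newcombe) interval.
2. For GIQLI, replace median and range with mean (SD) and median (quartiles) per group, in line with the opening sentence. Add the between-group mean difference with a 95% interval from an independent-groups analysis.
3. State that a non-significant result will be interpreted from its interval and not as evidence of no difference.
4. State that these unadjusted intervals show sampling error only and do not account for confounding by frailty.

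The cost is wording; no new data are needed. The downside is that the intervals will look wide.

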6. OBJECTIVES AND OUTCOME MEASURES

Objectives	Outcome Measures	Timepoint(s) of evaluation of this outcome measure (if applicable)
Primary Objective To compare the rate of gallstone- related hospital re-admission between patients treated operatively and non-operatively	Number and percentage of patients readmitted to hospital with gallstone-related disease by each timepoint.	30 days, 1 year, 3 years
1. To compare morbidity in operative and non-operative groups 2. To compare mortality in operative and non-operative groups 3. To compare quality of life in operative and non-operative groups	Number and percentage of patients with complications in each group Number and percentage of patients who have died in each group Gastrointestinal Quality of Life Index (GIQLI) in each group	30 days, 1 year, 3 years
Exploratory Objectives To assess the result of frailty on		

IRAS ID: 301556

morbidity, mortality and quality of	Morbidity, mortality and quality of life	30 days, 1 year, 3	l
life (as defined above)	according to Rockwood frailty score	years	l
To assess whether frailty affects	Comparison of Rockwood frailty score in		
whether or not surgery is carried	operative and non-operative groups both		
out	before and after surgery.		l
	- ,		

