7. TRIAL DESIGN

This is an observational multicentre cohort study which will take place in a number of hospitals in Wessex. Patients will be recruited to the trial during admission for gallstone disease and followed up for 3 years after this admission. At each follow up timepoint patients will be contacted and asked to complete a quality of life questionnaire and will also be asked whether they have had any further admissions with gallstone related disease. Follow up information may also be obtained from hospital and GP records where appropriate.

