9.6. Baseline Assessments

Demographic data will be collected from the participant's medical records. Frailty will also be assessed at baseline

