12.4. Analysis Populations

All patients as registered. Comparisons will be made between groups who had surgery during/after their index admission and those who were treated non-operatively in assessing the primary endpoint.

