13.2. Data Recording and Record Keeping

Data will be collected from medical records and direct patient questioning if necessary (e.g. in assessing frailty, if this information is not already available in the medical record). Quality of life data will be collected via a questionnaire sent to patients at 30 days, 1 year and 3 years. A named Surgical Registrar at each site

IRAS ID: 301556

will be responsible for data collection and CRF completion. Completed CRFs will be sent to the Wessex Research Collaborative and data will be entered onto Microsoft Excel.

The participants will be identified by a unique trial specific number in any database. The name and any other identifying detail will NOT be included in any trial data electronic file. Electronic CRFs will be kept for 5 years after recruitment has ended in case of need for re-review. Any concerns about incomplete or incorrect data will be discussed directly with the person responsible for data collection at the site and an attempt to verify the data will be made (e.g. through re-review of medical records).

All CRFs and data records in the database to be only identifiable by trial number. The list of trial numbers and link to patient details will be stored separately using fully secured computers within the research office of each site and will not be shared with the sponsoring organisation or the Wessex Research Collaborative.

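### A paired t-test is specified for quality of life between two groups of different, unmatched patients, so it cannot be run as written

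*Protocol*

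**What the plan says.** Section 6 of the Protocol sets the third secondary objective: "To compare quality of life in operative and non-operative groups". Section 12.2 gives the summary, "Gastrointestinal Quality of Life Index (GIQLI) in each group will be reported as a median and range", and then the test: "Paired T test will be used to compare groups".

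Four other places show what those groups are and when the data arise:

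- Section 7: "This is an observational multicentre cohort study". Section 9.4 confirms that there is no randomisation.
- Section 12.4 (written for the primary endpoint): "Comparisons will be made between groups who had surgery during/after their index admission and those who were treated non-operatively".
- Section 12.3: "the enrolment ratio is likely to be 1:9", non-operative to operative.
- Section 13.2: "Quality of life data will be collected via a questionnaire sent to patients at 30 days, 1 year and 3 years". Section 9.6 limits the baseline to demographic data and frailty ("Frailty will also be assessed at baseline").

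Section 12.1 says that the analysis plan is the one set out in section 12 and that no separate SAP document is used.

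**The concern.** A paired t-test works on within-pair differences. It needs each value in one group to be linked to one value in the other, because it comes from the same patient or a deliberately matched one. Here each patient belongs to one treatment group, and no link between patients in the two groups is defined.

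The analyst would have two choices. One is to substitute another test and report it as a deviation, as section 12.9 requires. The other is to invent a pairing that the Protocol does not describe. That would use at most as many operative patients as there are non-operative ones, and the result would depend on who happened to be paired with whom. Because section 12 is the only analysis plan, this is a wrong statement in the governing text, not a detail left for later.

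**Working it through.** **1. Can any reading supply pairs?**

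- *Matched patients.* Sections 7, 12.2 and 12.4 describe no matching.
- *Before and after treatment.* Sections 9.6 and 13.2 provide no baseline GIQLI.
- *Change within a patient between follow-ups.* This would be paired, but the sentence in section 12.2 compares groups, and so does the objective in section 6.

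None of the three fits the text.

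**2. Group sizes.** The Protocol gives no sample-size or precision figure for GIQLI, so there is none to reproduce. I take its total of 260 before loss to follow-up, which was set for the primary endpoint.

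- At 1:9 (section 12.3): 260 × 0.10 = 26 non-operative and 260 × 0.90 = 234 operative.
- At the upper non-operative share quoted in section 5, 30%: 260 × 0.30 = 78 and 260 × 0.70 = 182.

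A standard paired t-test routine given 26 and 234 values stops with an error because the lengths differ.

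**3. Illustration: what forced pairing would cost.** Assume a common standard deviation (SD) and pairs made from unrelated patients, so that the within-pair correlation is zero. With n₁ non-operative and n₂ operative patients:

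- Standard error from n₁ forced pairs: SD × √(2/n₁)
- Standard error from all patients as independent groups: SD × √(1/n₁ + 1/n₂)

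| Split | Operative patients discarded | Forced pairs | Independent groups | Ratio |
|---|---|---|---|---|
| 26 : 234 | 234 − 26 = 208 (89%) | √(2/26) = 0.277 SD | √(1/26 + 1/234) = 0.207 SD | 1.34 |
| 78 : 182 | 182 − 78 = 104 (57%) | √(2/78) = 0.160 SD | √(1/78 + 1/182) = 0.135 SD | 1.18 |

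The ratio depends only on the split, not on the total: √(2/(1 + n₁/n₂)) is √1.8 = 1.34 at 1:9 and √1.4 = 1.18 at 3:7.

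**4. The same loss as power, at 26 against 234.** This uses two-sided 0.05, the normal approximation and an assumed true difference of 0.5 SD.

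- Independent groups: Φ(0.5/0.2067 − 1.96) = Φ(0.459), about 68%.
- 26 forced pairs: Φ(0.5/0.2774 − 1.96) = Φ(−0.157), about 44%.

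The 0.5 SD is my assumption. The Protocol names no target difference for GIQLI.

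**The case against.** The best defence is that this is probably a slip of wording, paired for unpaired. No competent analyst would pair strangers. The software would refuse, an unpaired test would be used, and section 12.9 already provides for reporting the change. On that view the losses above would never happen. The point has force: the Protocol does not propose forced pairing, so those figures are illustrative. It does not remove the error, because the text cannot show that a slip was meant and no second document carries the right test.

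A reader might also infer several stronger criticisms that the document does not support:

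- *That a forced pairing gives an invalid standard error.* If unrelated patients were paired at random, the standard error would be valid for that subset. The cost is efficiency and reproducibility.
- *That the confidence interval would be 34% wider.* The 34% is a standard-error ratio. With t quantiles on 25 and 258 degrees of freedom, the interval would be about 40% wider (1.342 × 2.060/1.969 ≈ 1.40).
- *That GIQLI is summarised only by median and range.* Section 12.2 opens by promising the mean, standard deviation and quartiles for continuous data as well. Setting a test of means beside a median is at most a minor mismatch.
- *That the three timepoints are wrongly tested separately.* Section 12.2 does not say how they are tested, and comparing groups at each pre-stated timepoint is legitimate.
- *That GIQLI is in the study title.* The title names quality of life, not the instrument.

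**Conclusion.** The point holds. The test named for GIQLI does not fit the comparison it is meant to make: the groups are independent and no pairing is defined. Unequal size is secondary. It makes the test impossible to compute without dropping patients, but equal groups would not make it right either.

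If pairs were forced, the standard error would rise by about 18% to 34% as the non-operative share runs from 30% to 10%. Those figures assume a common SD, unrelated pairs and complete GIQLI data. The conclusion that the test is wrong needs none of these assumptions.

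This should be fixed, but it does not threaten the study. A reader might infer that the study's main result is at risk. It is not: GIQLI is a secondary outcome, and the primary readmission comparison, the sample size and the data collection are all unaffected.

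**What to change.** In section 12.2, replace the paired t-test with an independent-samples comparison of GIQLI between the operative and non-operative groups at each of 30 days, 1 year and 3 years. Either of these would do:

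- Welch's unpaired t-test, reporting the mean difference with its 95% confidence interval; or
- the Mann-Whitney test, if the median-and-range summary is to stay the main description.

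A mixed model over the three timepoints is optional and not needed to correct the error. It would require further decisions, such as which covariates to include and how GIQLI is handled after death.

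The simple replacement costs one sentence and the usual approval of a text amendment. It needs no new data and no change to recruitment or follow-up. Making it before analysis also avoids having to report a deviation under section 12.9.

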12.3. Sample Size Determination

From previous studies, we estimate an approximate readmission rate of at least 30% in patients who do not have surgery compared to 5% in those who do. We estimate that approximately 10% of patients over 70 will not have surgery therefore the enrolment ratio is likely to be 1:9. Using an alpha of 0.05 and a power of 0.9 the number of patients required would therefore be 260. We would aim to recruit a minimum of 290 patients to account for a maximum of 10% lost to follow up.

12.4. Analysis Populations

All patients as registered. Comparisons will be made between groups who had surgery during/after their index admission and those who were treated non-operatively in assessing the primary endpoint.

12.5. Decision Points

No interim analysis is planned.

12.6. Stopping Rules

N/A

12.7. The Level of Statistical Significance

The level of statistical significance will be set at 0.05.

12.8. Procedure for Accounting for Missing, Unused, and Spurious Data.

IRAS ID: 301556

Any concerns about incomplete or spurious data will be discussed directly with the person responsible for data collection at the site and an attempt to verify the data will be made (e.g. through re-review of medical records).

12.9. Procedures for Reporting any Deviation(s) from the Original Statistical Plan

Any deviation from the original statistical plan will be reported in any publication resulting from the trial.

12.10. Health Economics Analysis

N/A

13. DATA MANAGEMENT

The plan for the data management of the study are outlined below. There is not a separate Data Management document in use for the trial.

Source Data

Source documents are where data are first recorded, and from which participants' CRF data are obtained. These include, but are not limited to, hospital records (from which medical history and previous and concurrent medication may be summarised into the CRF), clinical and office charts, laboratory and pharmacy records, diaries, microfiches, radiographs, and correspondence.

CRF entries will be considered source data if the CRF is the site of the original recording (e.g. there is no other written or electronic record of data). All documents will be stored safely in confidential conditions. On all trial-specific documents, other than the signed consent, the participant will be referred to by the trial participant number, not by name.

13.1. Access to Data

Direct access will be granted to authorised representatives from the Sponsor, host institution and the regulatory authorities to permit trial-related monitoring, audits and inspections.

13.2. Data Recording and Record Keeping

Data will be collected from medical records and direct patient questioning if necessary (e.g. in assessing frailty, if this information is not already available in the medical record). Quality of life data will be collected via a questionnaire sent to patients at 30 days, 1 year and 3 years. A named Surgical Registrar at each site

IRAS ID: 301556

will be responsible for data collection and CRF completion. Completed CRFs will be sent to the Wessex Research Collaborative and data will be entered onto Microsoft Excel.

The participants will be identified by a unique trial specific number in any database. The name and any other identifying detail will NOT be included in any trial data electronic file. Electronic CRFs will be kept for 5 years after recruitment has ended in case of need for re-review. Any concerns about incomplete or incorrect data will be discussed directly with the person responsible for data collection at the site and an attempt to verify the data will be made (e.g. through re-review of medical records).

All CRFs and data records in the database to be only identifiable by trial number. The list of trial numbers and link to patient details will be stored separately using fully secured computers within the research office of each site and will not be shared with the sponsoring organisation or the Wessex Research Collaborative.

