9.7. Subsequent Visits

Patients will be contacted by telephone at 30 days, 1 year and 3 years from registration. Prior to any contact, the hospital EPR and CHiE will be checked to ensure that the patient is still alive.

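### No common pre-treatment GIQLI is collected and the groups are compared without adjustment, so a quality-of-life difference may reflect differences that existed before treatment

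*Protocol*

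**What the plan says.** The design is observational: "This is an observational multicentre cohort study which will take place in a number of hospitals in Wessex". One of the secondary objectives in section 6 is "To compare quality of life in operative and non-operative groups", measured with the GIQLI, and quality of life also appears in the study title.

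The synopsis, section 6 and section 13.2 all give the same three GIQLI times. In section 13.2: "Quality of life data will be collected via a questionnaire sent to patients at 30 days, 1 year and 3 years". Section 9.7 starts the clock at registration: "Patients will be contacted by telephone at 30 days, 1 year and 3 years from registration". Section 9.2 requires registration during the index admission.

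Section 9.6 contains two baseline items: "Demographic data will be collected from the participant's medical records", and "Frailty will also be assessed at baseline". Appendix A shows approach, consent and CRF completion at baseline, with no questionnaire named.

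For the analysis, section 12.2 says "Gastrointestinal Quality of Life Index (GIQLI) in each group will be reported as a median and range", followed by "Paired T test will be used to compare groups". No covariates are named, and section 12.1 says that no separate SAP is in use.

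**The concern.** In a non-randomised comparison, a difference in outcome can come from treatment or from who was selected for it. The protocol describes the selection itself: the lay summary says that patients not offered surgery are usually old, frail or have other illnesses. Section 6 has exploratory objectives on whether frailty affects the choice of surgery and how frailty relates to quality of life. The protocol thus treats frailty as possibly linked both to group and to this outcome.

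Without a score from before treatment, and without adjustment, a lower GIQLI in the non-operative group could simply mean that these patients were already worse off. The lay summary wants the results to inform discussions with patients about the likely outcomes of each option, so this reading matters. A score that was never collected cannot be recovered at the analysis stage.

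**Working it through.** **What is measured and when**

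| Item | Source | Content |
|---|---|---|
| Baseline data | Section 9.6, Appendix A | Demographics, frailty; no GIQLI named |
| GIQLI times | Synopsis, sections 6 and 13.2 | 30 days, 1 year, 3 years |
| Time origin | Sections 9.7 and 9.2 | Registration, during the index admission |
| Operative group | Section 12.4 | Surgery during or after the index admission |
| Operative group, primary endpoint | Section 12.2 | Management during the index admission |
| GIQLI analysis | Section 12.2 | Median and range, test without covariates |

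No section supplies a GIQLI common to all patients before treatment. Under section 12.4, a patient brought back for planned surgery more than 30 days after registration counts as operative but gives the 30-day score before the operation. The 30-day score is therefore neither a baseline nor a consistent post-treatment score. Sections 12.2 and 12.4 also need to be reconciled on who is operative.

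**Size of the carry-over (illustration)**

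The protocol states no GIQLI effect, SD or sample size, so there is no figure to reproduce. Assumptions not in the documents: equal SD in both groups and at both times, no effect of management, a pre-treatment gap of b SD, and correlation r between baseline and follow-up scores. The expected follow-up difference is then b × r SD.

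| Gap b | r = 0.3 | r = 0.5 | r = 0.6 |
|---|---|---|---|
| 0.2 SD | 0.06 | 0.10 | 0.12 |
| 0.5 SD | 0.15 | 0.25 | 0.30 |
| 0.8 SD | 0.24 | 0.40 | 0.48 |

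**What this does to a test**

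Section 12.3 expects a 1:9 ratio and 260 patients before losses, so 26 non-operative and 234 operative. For a test of two independent groups, the standard error in SD units is √(1/26 + 1/234) = √0.0427 = 0.207. With m = b × r / 0.207, the two-sided false-positive rate at a nominal 5% is Φ(m − 1.96) + Φ(−m − 1.96).

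| Gap b | r = 0.3 | r = 0.5 | r = 0.6 |
|---|---|---|---|
| 0.2 SD | 6% | 8% | 9% |
| 0.5 SD | 11% | 23% | 31% |
| 0.8 SD | 21% | 49% | 64% |

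Example: b = 0.5 and r = 0.5 give m = 0.25 / 0.207 = 1.21 and a rate of 23%. With 29 versus 261 patients (the recruitment target of 290) it is 25%.

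**Precision**

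Adjusting for a baseline score reduces residual variance by r²: 0.3² = 9%, 0.5² = 25%, 0.6² = 36%. The share that remains, 1 − r², is 91% to 64%.

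**The case against.** Several counter-arguments have force.

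- **The size is assumed.** Nothing in the documents says how far apart the groups are on a gastrointestinal score, and section 6 treats the effect of frailty on the choice of surgery as an open question. At a gap of 0.2 SD the carry-over is only 0.06 to 0.12 SD. This stands, which is why a range is shown.
- **Frailty is measured at baseline.** Rockwood score and age could absorb part of the imbalance. This is true of the data, but section 12.2 does not use them in the GIQLI comparison.
- **A baseline score may not be truly pre-treatment.** Section 9.2 sets no limit on the time of registration within the admission, so consent may follow an operation. The score is then retrospective, and recall may differ between groups. This stands and shapes the fix.
- **It may be late.** The synopsis plans recruitment from April 2022 to March 2023, and the logged amendment is dated 12 October 2022, about halfway. With even accrual (assumption) and 10% of 290 = 29 non-operative patients, about 29 / 2, or 14 to 15, would have remained, before deaths and non-return. If recruitment has closed, only the adjustment for existing data is possible.

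A reader might infer that every GIQLI is taken after treatment. Section 12.4 does not support that, because it counts later surgery as operative. A reader might also infer that a baseline GIQLI would by itself isolate the effect of management. It would not, because the reasons for choosing surgery go beyond prior quality of life.

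**Conclusion.** The point holds as a limit on interpretation. The protocol collects no common pre-treatment GIQLI and plans an unadjusted comparison of groups that it describes as differing in age, frailty and comorbidity. Followed as written, a GIQLI difference cannot be read as an effect of management.

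Under the assumptions above, the spurious difference is 0.06 to 0.48 SD, or 0.15 to 0.30 SD at a gap of 0.5 SD. Those figures illustrate the mechanism and do not estimate what will happen in this study. A secondary objective is affected. Readmission, which is the primary endpoint and the basis of the sample size, is not. The change is worth making because part of it needs no new data.

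**What to change.** 1. In section 12.2, replace the GIQLI comparison with a between-group model at each time point, adjusted for baseline Rockwood score and age. This also removes the paired test, which does not suit two separate groups of patients. It needs no new data and is possible even if recruitment has closed.
2. For patients still to be registered, add a GIQLI at consent to sections 9.6 and 13.2 and Appendix A, referring to the period before the acute episode. Record whether it was completed before or after any operation in the index admission. Adjust for it in a subset or sensitivity analysis, and say that the non-operative part of that subset may be very small.
3. State that GIQLI differences are associations, because confounding by indication remains. Say also that the 30-day score precedes the operation in some patients with delayed surgery, and reconcile sections 12.2 and 12.4 on group membership.

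Cost: a minor amendment and one more completion of a questionnaire already in use. The downside is a few minutes for an acutely ill patient, and recall error that may differ between groups when consent follows surgery.
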